10.5. Appendix 5: Derived and Transformed Data

10.5.1. General

Multiple Measurements at One Time Point

- Mean of the measurements will be calculated and used in any derivation of summary statistics but if listed, all data will be presented.
- The worst finding/interpretation associated with multiple measurements as the finding/interpretation for that time point.
- Subjects having both High and Low values for Normal Ranges at any post-baseline visits for safety parameters will be counted in both the High and Low categories of “Any visit post-baseline” row of related summary tables. This will also be applicable to relevant Potential Clinical Importance summary tables.

Study Day

- Calculated as the number of days from Treatment start date:
 - Ref Date = Missing → Day = Missing
 - Ref Date < Treatment start Date → Study Day = Ref Date – Treatment start Date
 - Ref Date ≥ Treatment start Date → Study Day = (Ref Date – Treatment start Date) + 1

10.5.2. Study Population

Demographics

Age

- GSK standard IDSL algorithms will be used for calculating age where birth date will be imputed as follows:
 - Any subject with a missing day will have this imputed as day ‘15’.
 - Any subject with a missing date and month will have this imputed as ‘30th June’.
- Birth date will be presented in listings as ‘YYYY’.

Body Mass Index (BMI)

- Calculated as **Weight (kg) / [Height (m)]²**

10.5.3. Safety

Laboratory Parameters

- If a laboratory value which is expected to have a numeric value for summary purposes, has a non-detectable level reported in the database, where the numeric value is missing, but typically a character value starting with ‘<x’ or ‘>x’ (or indicated as less than x or greater than x in the comment field) is present, the number of decimal places in the observed values will be used to determine how much to add or subtract in order to impute the corresponding numeric value.
 - Example 1: 2 Decimal Places = ‘< x’ becomes x – 0.01
 - Example 2: 1 Decimal Places = ‘> x’ becomes x + 0.1

Laboratory Parameters

- Example 3: 0 Decimal Places = '< x' becomes x – 1

ECG Parameters**RR Interval**

- IF RR interval (msec) is not provided directly, then RR can be derived as :
[1] If QTcB is machine read & QTcF is not provided, then :

$$RR = \left[\left(\frac{QT}{QTcB} \right)^2 \right] * 1000$$

- [2] If QTcF is machine read and QTcB is not provided, then:

$$RR = \left[\left(\frac{QT}{QTcF} \right)^3 \right] * 1000$$

- If ECGs are manually read, the RR value preceding the measurement QT interval should be a collected value THEN do not derive.
- Machine read values of RR should not be replaced with derived values.

Corrected QT Intervals

- When not entered directly in the eCRF, corrected QT intervals by Bazett's (QTcB) and Fredericia's (QTcF) formulas will be calculated, in msec, depending on the availability of other measurements.
- IF RR interval (msec) is provided then missing QTcB and/or QTcF will be derived as :

$$QTcB = \frac{QT}{\sqrt{\frac{RR}{1000}}}$$

$$QTcF = \frac{QT}{\sqrt[3]{\frac{RR}{1000}}}$$

AEs**AEs OF Special Interest**

- Thrombosis and/or tissue ischemia secondary to excessive erythropoiesis
- Death, MI, stroke, heart failure, thromboembolic events, thrombosis of vascular Access
- Cardiomyopathy
- Pulmonary artery hypertension
- Cancer-related mortality and tumour progression and recurrence
- Esophageal and gastric erosions
- Proliferative retinopathy, macular edema, choroidal neovascularization
- Exacerbation of rheumatoid arthritis

10.6. Appendix 6: Premature Withdrawals & Handling of Missing Data

10.6.1. Premature Withdrawals

Element	Reporting Detail
General	
 • A completed subject is one who has completed all phases of the study including the follow-up visit. • Withdrawn subjects may be replaced in the study. • All subjects who withdraw prematurely from the study will be documented and the reason for their withdrawal recorded in the final Clinical Pharmacology Study Report (CPSR). • All available data collected up until the point of withdrawal, and the follow-up visits will be used in the analyses and will be listed and all available planned data will be included in the summaries according to the populations defined in Section 4 unless otherwise specified.

10.6.2. Handling of Missing Data

Element	Reporting Detail
General	
 • Missing data occurs when any requested data is not provided, leading to blank fields on the collection instrument: 
 • These data will be indicated by the use of a “blank” in subject listing displays. Unless all data for a specific visit are missing in which case the data is excluded from the table. • Answers such as “Not applicable” and “Not evaluable” are not considered to be missing data and should be displayed as such.
Outliers	
 • Any subjects excluded from the summaries and/or statistical analyses will be documented along with the reason for exclusion in the clinical study report.

10.6.2.1. Handling of Missing Dates

Element	Reporting Detail
General	Partial dates will be displayed as captured in subject listing displays.
Adverse Events	
 • The eCRF allows for the possibility of partial dates (i.e., only month and year) to be recorded for AE start and end dates; that is, the day of the month may be missing. In such a case, the following conventions will be applied for calculating the time to onset and the duration of the event: 
 • Missing Start Day: First of the month will be used unless this is before the start date of investigational product; in this case the study treatment start date will be used (and hence the event is considered On-treatment as per

Element	Reporting Detail
	
Appendix 3: Treatment States).
 
 
• Missing Stop Day: Last day of the month will be used, unless this is after the stop date of study treatment; in this case the study treatment stop date will be used. 
• Completely missing start or end dates will remain missing, with no imputation applied. Consequently, time to onset and duration of such events will be missing. 
• AEs with entirely missing or unknown start dates will be assumed to be on-treatment for reporting. 
• AEs with missing end dates are not anticipated to affect reporting.

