### **9.2.3. Follow-up of AEs and SAEs**

After the initial AE/SAE report, the investigator is required to proactively follow each participant at subsequent visits/contacts. All SAEs, and non serious AEs of special interest (as defined in Section 9.2.4), will be followed until the event is resolved, stabilized, otherwise explained, or the participant is lost to follow-up (as defined in Section 8.3). Further information on follow-up procedures is given in [Appendix 6](#).

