2.2. Study Design

Overview of Study Design and Key Features	
Design Features	
A phase 1, open-label, non-randomized, parallel group, single-dose adaptive study in adults with moderate (Part 1) and either mild or severe (Part 2) hepatic impairment and matched, healthy control participants with normal hepatic function.
 
Part 1:
 
Part 1 will include 2 cohorts. Cohort 1 includes participants with moderate hepatic impairment, and Cohort 2 includes matched healthy control participants.
 
Healthy control participants (n=8) will be matched in gender, age (± 10 years), and BMI ($\pm 15\%$) to participants with moderate hepatic impairment (n=8; Child-Pugh score of 7-9).
 
All participants will receive 6 mg of daprodustat as a single oral dose in the fasted state.
 
Up to 16 participants (8 in each cohort, excluding possible replacements) will be recruited into Part 1 of the study.
 
Part 2:
 
Part 2 will include 2 cohorts. Cohort 3 includes participants with either mild or severe hepatic impairment, and Cohort 4 includes matched healthy control participants.
 
Healthy control participants (n=8) will be matched in gender, age (± 10 years), and BMI ($\pm 15\%$) to participants with either mild impairment (Child-Pugh score of 5-6) or participants with severe impairment (Child-Pugh score of 10-13) (n=8).
 
All participants will receive 6 mg of daprodustat as a single oral dose in the fasted state.
 
Up to 16 participants (8 in each cohort, excluding possible replacements) will be recruited into Part 2 of the study.
 
All participant's total involvement with the study will be up to 7 weeks.

Dosing	
Part 1
 
All participants will be administered 6 mg of daprodustat as a single oral dose, with assessments conducted for up to 48 h post dosing (Please refer to Appendix 2)

Overview of Study Design and Key Features	
	
Part 2
 
If conducted, all participants will be administered 6 mg of daprodustat as a single oral dose, with assessments conducted for up to 48 h post dosing.

Treatment Assignment	
 • Part 1 consists of up to 16 participants (8 in each cohort, excluding possible replacements). • Part 2 consists of up to 16 participants (8 in each cohort, excluding possible replacements). • All participants will receive the same treatment of a single oral 6 mg dose of daprodustat.

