8.1. Overview of Planned Adverse Events Analyses

Adverse Events will be coded using Medical Dictionary for Regulatory Activities (MedDRA) central coding dictionary and summarized by cohort.

Counting of AEs will be based on the number of subjects – not the number of AEs. For example, if a subject experiences the same AE (i.e. same preferred term) more than once, they are counted only once under the count for the preferred term. If a subject experiences more than one AE in a particular system organ class (SOC), they will only be included once in the count for the SOC, but will appear in the count for each appropriate preferred term within the SOC. Therefore, the sum of the numbers of subjects with each preferred term event within a SOC may exceed the total number of subjects with at least one event.

[Table 7](#) provides an overview of the planned analyses, with further details of data displays being presented in [Appendix 10](#): List of Data Displays.

Table 7 Overview of Planned Adverse Event Analyses

Endpoint / Parameter/ Display Type	Absolute		
	Summary		Individual
	T	F	L
Adverse Events (AEs)			
All AEs	Y		Y
Serious AEs	Y		Y
Drug Related AEs	Y		Y
AEs leading to withdrawal	Y		Y
Summary of Common (>=25%) Non-serious Adverse Events by System Organ Class and Preferred Term	Y		
Serious Adverse Events by System Organ Class and Preferred Term (Number of Subjects and Occurrences)	Y		
Relationship Between System Organ Class and Verbatim Text			Y
Subject Numbers for Individual Adverse Events			Y
AEs of special interest ^[1]			Y

NOTES:

- T = Table, F = Figures, L = Listings, Y = Yes display generated
- Summary = Represents TF related to any summaries (i.e. descriptive statistics) of the observed raw data.
- Individual = Represents FL related to any displays of individual subject observed raw data.

^[1] Conditional displays, if data is available listing will be generated.

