10.2. Appendix 2: Time & Events

10.2.1. Protocol Defined Time & Events

Procedure	Screening ¹	Day -1	Pre-Dose	0 h	0.5 h	1 h	1.5 h	2 h	3 h	4 h	6 h	8 h	10 h	12 h	24 h	36 h	48 h	Follow-up ²
Informed Consent	X																	
Inclusion & Exclusion Criteria	X	X																
Demography	X																	
Full physical exam	X																	
Medical history	X																	
Past/current medications	X																	
Laboratory assessments ³	X																X	X
Drug/Alcohol Screen	X	X																
12-lead ECG	X	X															X	X
Vital Signs and Weight	X	X															X	X
Pregnancy Test	X ⁴	X ⁴																
Females only: Estrogen and FSH ⁵	X																	

CONFIDENTIAL

200231

Procedure	Screening ¹	Day -1	Pre-Dose	0 h	0.5 h	1 h	1.5 h	2 h	3 h	4 h	6 h	8 h	10 h	12 h	24 h	36 h	48 h	Follow-up ²
Admission to Unit		X																
Brief Physical Exam		X															X	X
Administration of daprodustat				X														
PK blood sampling			X		X	X	X	X	X	X	X	X	X	X	X	X	X	
Protein binding sample			X						X					X	X			
EPO blood sampling			X		X	X	X	X	X	X	X	X	X	X	X	X	X	
Adverse Events Assessment	X	X	X	X	X	X	X	X	X	X	X	X	X	X	X	X	X	X
Review Concomitant Medications		X	X												X		X	X
Discharge from Unit																	X	

¹ All participants will undergo screening assessments within 28 days of enrolment.

² A follow-up visit will occur 10-14 days after the dose of study treatment.

³ Laboratory assessment guidance can be found in Protocol Appendix 3.

⁴ For women of childbearing potential that are not using an approved method of contraception (see Protocol Appendix 6), one negative pregnancy test between Day -7 and Day -4 AND another negative pregnancy test on Day -1 is required. Additional guidance can be found in Protocol Section 9.5.5.

⁵ All females are to have estrogen and FSH measured at screening.

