10.3. Appendix 3: Treatment States

10.3.1. Treatment States for AE Data

Assessments and events will be classified according to date of occurrence relative to the start and/or stop date of the study treatment.

Treatment State	Definition
Pre-Treatment	Date < Study Treatment Start Date
On-Treatment	If AE onset date is on or after treatment start date & on or before the treatment stop date + 2 days $\text{Study Treatment Start Date} \leq \text{AE Start Date} \leq \text{Study Treatment Stop Date} + 2 \text{ days}$
Post-Treatment	If AE onset date is after the treatment stop date + 2 days $\text{AE Start Date} > \text{Study Treatment Stop Date} + 2 \text{ days}$
AE Onset Time Since First Dose (Days)	If Treatment Start Date > AE Onset Date = AE Onset Date - Treatment Start Date If Treatment Start Date \leq AE Onset Date = AE Onset Date - Treatment Start Date + 1 day Missing otherwise
AE Duration (Days)	AE Resolution Date – AE Onset Date + 1 day
AE Drug-related	If relationship is marked 'YES' on eCRF or value is missing.

NOTES:

- If the study treatment stop date is missing, then the AE will be considered to be On-Treatment.

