10.6.2.2. Handling of Partial Dates

Element	Reporting Detail
Concomitant Medications	
 
• Partial dates for any concomitant medications recorded in the CRF will be imputed using the following convention: 
 
• If the partial date is a start date, a '01' will be used for the day and 'Jan' will be used for the month 
• If the partial date is a stop date, a '28/29/30/31' will be used for the day (dependent on the month and year) and 'Dec' will be used for the month. 
• The recorded partial date will be displayed in listings.
Adverse Events	
 
• Any partial dates for adverse events will be raised to data management. If the full date cannot be ascertained, the following assumptions will be made for calculating the time to onset and the duration of the event: 
 
• If the partial date is a start date, a '01' will be used for the day and 'Jan' will be used for the month, unless this is before the start date of investigational product; in this case the study treatment start date will be used (and hence the event is considered on-treatment as per Appendix 3: Treatment States). 
• If the partial date is a stop date, a '28/29/30/31' will be used for the day (dependent on the month and year) and 'Dec' will be used for the month, unless this is after the stop date of study treatment; in this case the study treatment stop date will be used. 
• The recorded partial date will be displayed in listings.

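### Partial AE stop dates are capped at the single dosing date, so a Day 2 onset gets a duration of 0 days and any later onset a negative one

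*SAP*

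**What the plan says.** The amended SAP handles partial AE dates in two places. Section 10.6.2.1 covers a missing day. The stop date becomes the last day of the recorded month, "unless this is after the stop date of study treatment; in this case the study treatment stop date will be used". Section 10.6.2.2 covers a missing day and month: the stop date goes to the end of the year, with the same cap. The first SAP (based on the May 2017 protocol) has the same two rules, so the amendment did not touch them.

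The purpose is explicit: "the following conventions will be applied for calculating the time to onset and the duration of the event". Section 10.3.1 defines duration as "AE Resolution Date – AE Onset Date + 1 day".

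On the design, section 2.2 states: "All participants will receive the same treatment of a single oral 6 mg dose of daprodustat". The schedule in 10.2.1 adds: "A follow-up visit will occur 10-14 days after the dose of study treatment". Protocol 9.2.1 collects AEs from dosing to that visit.

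**The concern.** A cap at the end of treatment may do little harm where dosing runs for weeks. Here treatment starts and stops on the same day, while AEs are collected for another 10 to 14 days. The cap therefore pulls the end of nearly every imputed event back to before it began. Neither section says that an imputed stop date may not precede onset. A programmer following the text would produce zero or negative durations, and would either report them or have to depart from the plan.

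**Working it through.** **Inputs**

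- Cap on the stop date: SAP 10.6.2.1 and 10.6.2.2.
- Duration = resolution - onset + 1: SAP 10.3.1.
- One dose per participant: SAP 2.2. The treatment stop date is not defined in words; with a single dose it is taken to be the dosing date.
- Dosing date = Study Day 1: SAP 10.5.1.
- Follow-up 10 to 14 days after the dose, which is Study Day 11 to 15: SAP 10.2.1.

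The plan states no figure on this point, so there is none to reproduce.

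**Known onset, partial stop date**

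For a post-dose event, the last day of the recorded stop month or year can never fall before the dosing date. It is either later, and the cap resets it to Day 1, or it is the dosing date itself. The imputed stop is Day 1 in both cases, so for onset on Day d (d at least 1):

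duration = 1 - d + 1 = 2 - d

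| Onset day | Imputed stop | Duration (days) |
|---|---|---|
| 1 | Day 1 | 1 |
| 2 | Day 1 | 0 |
| 3 | Day 1 | -1 |
| 5 | Day 1 | -3 |
| 11 | Day 1 | -9 |
| 15 | Day 1 | -13 |

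The true duration of an event that starts on Day 2 and resolves by a Day 15 follow-up is 1 to 14 days.

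Example: dosing on 10 May, onset 12 May (Day 3), stop recorded only as May. 31 May is after 10 May, so the stop becomes 10 May and the duration is 10 - 12 + 1 = -1. Dosing at a month end does not help. With dosing on 31 May, onset 1 June (Day 2) and stop recorded as June, the stop becomes 31 May and the duration is 0.

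**Enumeration**

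For follow-up on Day 11, 12, 13, 14 or 15 there are 66 + 78 + 91 + 105 + 120 = 460 pairs of onset and resolution up to follow-up. Over 365 dosing dates that is 460 x 365 = 167,900 combinations. Every one gives 2 - d, under both the missing-day and the missing-month rule. This confirms the algebra and adds nothing to it.

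**Start day also missing**

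If the event is recorded in the dosing month, onset is imputed to Day 1 and duration is 1. If it is recorded in the following month, onset is imputed to the first of that month and the result is again 0 or negative. With dosing on 25 January and both dates recorded as February, onset is 1 February (Day 8) and duration is 2 - 8 = -6.

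**The case against.** The strongest reply is that nothing reported is shown to depend on this.

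- **Outputs.** On AE tables the SAP says "Counting of AEs will be based on the number of subjects". Treatment state is set by onset, Tables 2.1 to 2.6 name no duration, and for listings 10.6.2.2 says "The recorded partial date will be displayed in listings". Section 10.6.2.1 also expects missing end dates to have no effect on reporting. All of this limits the damage. It does not repair a rule that both sections say is used to calculate duration.
- **Frequency.** Participants are resident until 48 h with AE checks at each nominal time, partial dates are first queried with data management, and completely missing end dates are not imputed. The trigger is therefore rare. That stands, but the rule exists for the cases where the query fails.
- **Scope.** The formula holds only for onset from Day 1 on. Study-related SAEs are recorded from consent, and for a pre-dose onset the cap does not give a negative duration. It also needs a recorded treatment stop date. Both limits are accepted.
- **Remedy.** Imputing the latest possible date can overstate an event's length, and last contact is not defined in the SAP. A simpler repair is to leave duration missing for unresolved partial stop dates, as is already done for completely missing ones. That would also remove the impossible values, but it discards the recorded month.

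**Conclusion.** The concern holds. In this single-dose study the rule gives 0 days for a known onset on Day 2 and a negative duration for every later onset, down to -13 days for Day 15. A Day 1 onset always gets exactly 1 day. The failure begins inside the SAP's own on-treatment window, which runs to Day 3.

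The conclusion rests on reading the treatment stop date as the dosing date. Whether derived duration appears in the AE listings is unknown, because the listing columns are not shown. The number of events affected cannot be estimated from the documents. PK and PD endpoints, AE incidence and the Part 2 decision are untouched. It is an error worth correcting, at low priority.

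**What to change.** In SAP 10.6.2.1 and 10.6.2.2, remove the treatment-stop cap for AE stop dates. Impute the last possible day of the recorded month or year, capped at the participant's last-contact date, and never earlier than the later of AE onset and the first day of the recorded month or year. Define last contact. Section 10.6.2.2 already imputes concomitant-medication stop dates without a treatment-stop cap.

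The floor at onset guarantees a duration of at least 1 day. The floor at the start of the recorded period is needed because, under Protocol 9.2.3, SAEs and AEs of special interest "will be followed until the event is resolved, stabilized, otherwise explained, or the participant is lost to follow-up". A recorded stop month can therefore fall after the follow-up visit. For example, with onset on 20 May, last contact entered as 24 May and stop recorded as June, the cap alone would give 24 May; the floor moves it to 1 June, a duration of 13 days.

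Over the same 167,900 combinations the proposed rule gives no duration below 1 day and no imputed date outside the recorded month. For a missing day it places the stop 0 to 14 days late. That enumeration ends at the follow-up visit; later contacts rely on the floor argument above.

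The cost is one sentence in each of two SAP sections, the last-contact definition, and a minor change to the derivation code.

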10.6.2.2. Handling of Partial Dates

Element	Reporting Detail
Concomitant Medications	
 
• Partial dates for any concomitant medications recorded in the CRF will be imputed using the following convention: 
 
• If the partial date is a start date, a '01' will be used for the day and 'Jan' will be used for the month 
• If the partial date is a stop date, a '28/29/30/31' will be used for the day (dependent on the month and year) and 'Dec' will be used for the month. 
• The recorded partial date will be displayed in listings.
Adverse Events	
 
• Any partial dates for adverse events will be raised to data management. If the full date cannot be ascertained, the following assumptions will be made for calculating the time to onset and the duration of the event: 
 
• If the partial date is a start date, a '01' will be used for the day and 'Jan' will be used for the month, unless this is before the start date of investigational product; in this case the study treatment start date will be used (and hence the event is considered on-treatment as per Appendix 3: Treatment States). 
• If the partial date is a stop date, a '28/29/30/31' will be used for the day (dependent on the month and year) and 'Dec' will be used for the month, unless this is after the stop date of study treatment; in this case the study treatment stop date will be used. 
• The recorded partial date will be displayed in listings.

